9.4.2.2 Part 1B: Preliminary Food Effect Assessment

Part 1B may start once the RDE has been defined in Part 1A. M4076 will be administered at a dose and schedule that was determined as the RDE in Part 1A.

The SMC will continue to monitor the safety of M4076 during Part 1B. The SMC will be supported by the results of the Bayesian model used in Part 1A. During Part 1B, the model will support the SMC e.g. when a change in dose is considered by providing toxicity estimates for the doses. Unacceptable toxicity in the food effect cohort is defined as AEs that meet the DLT criteria (as defined in Section 6.6) regardless of when they occur during treatment.

9.4.3 Other Analyses

Details on the PK, **CC** and **CCI** biomarker analyses will be in the iAP that will be finalized before database lock. Integrated analyses across studies, such as the population PK analysis and PD analyses will be presented separately from the main CSR.

PK parameters will be calculated using standard non-compartmental methods and the actual administered dose. PK parameters will be calculated using the actual elapsed time postdose, with the exception of PK analysis for SMC review, which will be calculated using scheduled sampling times (see [Table 19](#)). Where the actual sampling time is missing the calculations may be performed using the scheduled sampling times.

Noncompartmental analysis will be performed using Phoenix® WinNonlin® (Certara, L.P., [name]) Version 6.3 or higher.

The statistical software SAS® (Statistical Analysis System, SAS-Institute, Cary, NC, USA windows Version 9.4 or higher) may be used to produce tables listings and figures.

Table 19 **Part 1 - Other Analyses**

Other Analyses	Part 1A: Dose Escalation
C_{max} , $C_{max}/Dose$, t_{max} , $AUC_{0-tlast}$, $AUC_{0-tlast}/Dose$, $AUC_{0-\infty}$, $AUC_{0-\infty}/Dose$, $t_{1/2}$, AUC_{τ} , $AUC_{\tau}/Dose$, CL/F , V_z/F C_{trough} , $R_{acc}(AUC_{\tau})$, $R_{acc}(C_{max})$, LI , t_{last}	PK parameters of M4076 (in plasma) after single and multiple dose (monotherapy) will be calculated by noncompartmental analysis. Summary statistics of PK parameters and associated PK concentrations will be determined and reported. Analyses will be performed on the PKAS.
	Part 1B: Preliminary Food Effect Assessment
$AUC_{0-tlast}$, C_{max} , $AUC_{0-\infty}$	PK parameters of M4076 will be calculated after single dose using noncompartmental analysis. A mixed model with study intervention, period and sequence as fixed effects and a random effect for participant within sequence will be applied to log-transformed PK parameters C_{max} and AUC_{τ} . Analyses will be based on the PKAS.
$C_{max}/Dose$, t_{max} , $AUC_{0-tlast}/Dose$, $AUC_{0-\infty}/Dose$, $t_{1/2}$, AUC_{τ} , $AUC_{\tau}/Dose$, AUC_{0-72} , $AUC_{0-72}/Dose$, CL/F , V_z/F C_{trough} , $R_{acc}(AUC_{\tau})$, $R_{acc}(C_{max})$, LI , t_{last} , CLR , $A_e(t_{1-t2})$, $f_e(t_{1-t2})$	Additional M4076 PK parameters (plasma and urine) and summary statistics.
Concentration-QTc	Relationship of time matched PK concentration to change from baseline QTc will be explored by concentration-QT analysis. This analysis may include PK time-matched QTc data from other M4076 clinical studies. The details of this analysis will be described in a separate analysis plan, and the results reported separately from the CSR.

FAS = full analysis set; PK = pharmacokinetic; PKAS = pharmacokinetic analysis set; QTc = corrected QT interval; R_{acc} = accumulation ratio.

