9.3 Populations for Analyses

The analysis populations are specified below (Table 15). The final decision to exclude participants from any analysis population will be made during a data review meeting prior to database lock. However, for the DLT analysis set, the decision on evaluability will be made by the SMC.

Table 15 Populations for Analyses

Analysis Set	Description
Screening (SCR)	All participants, who provided informed consent.
Full Analysis Set (FAS) / Safety Analysis Set (SAF)	All SCR participants, who received at least one dose of any study intervention. Analyses will consider participants as treated.
DLT	All FAS/SAF participants who meet at least one of the following criteria: 
Experienced at least one DLT during the DLT period, regardless of the administered number of doses of study intervention/completion of the DLT period.Received at least 80% of the planned cumulative dose during the DLT period of each study intervention and completed the DLT period.Additionally, participants who did not receive 80% of the planned total dose of study intervention, but at least 80% dosing of a different dose cohort and finished the DLT period are eligible for the DLT analysis set to be analyzed in the highest dose cohort for which they received 80% of dosing. The final decision on evaluability for dose escalation analysis will be made by the SMC (e.g. considering relevant deviations from dosing schedule).
PK (PKAS)	All participants who receive at least one dose of study intervention and provide at least one measurable post-dose concentration. A measurement below lower limit of quantification (BLQ) is considered a valid measurement. Participants will be analyzed according to the actual treatment they received. All PK analyses will be based on the PK Analysis Population.
Pd	All participants, who receive at least one dose of study intervention, have no clinically important protocol deviations or important events affecting Pd, and provide at least one measurable Pd endpoint postdose. Participants will be analyzed per the actual study intervention they received. All Pd analyses will be based on this analysis population.

DLT = dose limiting toxicity; Pd = pharmacodynamics; PK = pharmacokinetics; PKAS = pharmacokinetic analysis set.

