### PK Analysis Set (PKAS)

The Pharmacokinetic (PK) Analysis Set (PKAS) is a subset of the FAS/SAF and will consist of all participants, who receive at least one dose of study intervention, and provide at least one measurable post-dose concentration. A measurement below lower limit of quantification (BLQ) is considered a valid measurement. Participants will be analyzed per the actual study intervention they received. All PK analyses will be based on the PK Analysis Population.

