### 16.1.3 Statistical Analysis of PK Parameter Data

Dose proportionality will be provided separately for  $AUC_{0-\infty}$ ,  $AUC_\tau$ ,  $AUC_{0-tlast}$  and  $C_{max}$  on study day 1 and 8 for Part 1A using a power model. The power model will have the form:

$$Y = a * (dose)^b$$

where Y is the PK parameter, and a and b are the coefficient and exponent, respectively, of the power equation. By taking the natural logarithm (ln), the power model can be analysed using linear regression and has the form:

$$\ln(Y) = \ln(a) + b * \ln(dose) + \text{error}$$

$$= \alpha + \beta * \ln(dose) + \text{error},$$

where  $\alpha$  is the intercept, and  $\beta$  is the slope, and  $\ln(dose)$  is based on the dose size for each subject. For each PK parameter, the point estimate of slope  $\beta$  and its 95% CI will be provided. In addition, the estimated regression line will be overlaid on the individual points in the corresponding scatter plot (log-log scale).

Dose proportionality will be declared if the 90% confidence interval (CI) for  $\beta$  is entirely contained within the critical region,

$$\left( 1 + \frac{\ln(0.50)}{\ln(r)}, 1 + \frac{\ln(2.00)}{\ln(r)} \right)$$

where  $r$  is the ratio of the highest and the lowest dose in a given part of the study. Dose proportionality for participants who were administered the study intervention will be tested for  $C_{max}$  and  $AUC_{0-\infty}$ ,  $AUC_\tau$ ,  $AUC_{0-tlast}$  on Day 1 and at steady state.

Since the study is neither optimally designed nor powered to confirm the presence or absence of meaningful departures from dose proportionality, these results should be interpreted with caution. In addition, graphical assessment would also be considered to understand dose proportionality.

If the samples remain above LLOQ for the whole dosing interval, then  $AUC_{0-t_{last}}$  will be the same as  $AUC_{\tau}$  for Part 1A as there is another dose after 24 hours

A statistical analysis will be conducted to investigate the food effect on the treatment by comparing (fed) treatment to (fasted) treatment for Part 1B.

The natural log (ln)-transformed  $AUC_{0-\infty}$ ,  $AUC_{\tau}$ ,  $AUC_{0-t_{last}}$  and  $C_{max}$  will be analyzed using a mixed effect model. The model will include planned treatment sequence, period, and actual treatment as fixed effects, and subject within planned treatment sequence as a random effect.

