#### **16.1.4 General Specifications for PK Concentration and PK Parameter Data**

Predose samples that occur before the first or subsequent drug administration will be assigned a time of 0 hours, as if the sample had been taken simultaneously with the study intervention administration.

Predose or trough samples which have been taken after the subsequent dosing will be reported as a protocol deviation. The resulting concentrations will be included in concentration listings but excluded from descriptive statistics of concentrations and from PK parameter estimation.

Values below the lower limit of quantification (BLQ) will be taken as zero for summary statistics of PK concentration data, PK parameter estimation (e.g. AUC) and for graphical presentations.

In case profiles have a measurable pre-dose concentration less than or equal to 5% of its  $C_{max}$  value, the participant's data will be included in the PK and statistical analyses without any adjustments. If the pre-dose value is greater than 5% of the  $C_{max}$ , the participant's data for the affected profile will be included in the PK evaluation but excluded from descriptive and further statistical evaluation after agreement with the sponsor.

Missing concentrations (e.g. no sample, insufficient sample volume for analysis, no result or result not valid) will be reported and used generally as "N.R.". A participant who withdraws prior to the last planned observation will be included in the analyses up to the time of discontinuation.

Samples that are collected outside with a time deviation of > 10% from the protocol-scheduled time will be included in the PK parameter estimation (NCA) but will be excluded from the concentration summary and mean/median concentration plots.

PK concentrations which are erroneous due to a sampling processing or analytical error (as documented in the bioanalytical report) may be excluded from the PK analysis if agreed by the Sponsor. In this case the rationale for exclusion will be provided in the CSR. Any other PK concentrations that appear implausible to the Clinical Pharmacologist/Clinical PK/PD Scientist will generally not be excluded from the analysis and data handling will be agreed with the sponsor clinical pharmacologist/PK scientist. Any implausible data will be documented in the CSR.

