If AUC0-∞ cannot be determined reliably for all subjects and/or dose levels/treatments, an alternative AUC measure, such as AUC to a fixed timepoint or AUC0-tlast, may be used in the statistical analysis of dose proportionality and/or food effect.

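### SAP 16.1.3 compares AUC0-tlast fed versus fasted without a common sampling window, so terminal samples missed in one period can shift the ratio or widen its interval

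*Protocol*

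**What the plan says.** Protocol 9.4.3 (Table 19) lists AUC0-tlast, Cmax and AUC0-inf as the food-effect parameters. It plans a crossover analysis: "A mixed model with study intervention, period and sequence as fixed effects and a random effect for participant within sequence will be applied". The model sentence in that cell names only Cmax and AUCtau. On the analysis set it says "Analyses will be based on the PKAS".

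The SAP is more explicit. Section 16.1.3 models log AUC0-inf, AUCtau, AUC0-tlast and Cmax: "The model will include planned treatment sequence, period, and actual treatment as fixed effects, and subject within planned treatment sequence as a random effect". AUC0-tlast, AUC0-inf and Cmax are the endpoints declared in the objectives tables of both documents; AUCtau is modelled but not declared.

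Entry to the PK analysis set is light. Protocol 9.3 takes "All participants who receive at least one dose of study intervention and provide at least one measurable post-dose concentration", and SAP 8.1 adds "A measurement below lower limit of quantification (BLQ) is considered a valid measurement". On early stopping, SAP 16.1.4 says: "A participant who withdraws prior to the last planned observation will be included in the analyses up to the time of discontinuation".

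SAP 16.1.5.1 ends AUC0-tlast at the last quantifiable sample. It excludes terminal-phase parameters (half-life, AUC0-inf, CL/F) from statistical evaluation if extrapolation exceeds 20%, adjusted R-squared is below 0.8, or the regression spans less than two half-lives. If AUC0-inf is not reliable, an alternative "may be used in the statistical analysis of dose proportionality and/or food effect"; the two examples given are AUC to a fixed timepoint and AUC0-tlast.

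**The concern.** A crossover ratio of AUC0-tlast compares like with like only if both periods of a participant cover the same time span. The plan provides for that in its sampling schedule but not in its analysis rules. If a participant completes one period to 72 h and stops at 24 h in the other, the model receives roughly AUC0-72 on one side and AUC0-24 on the other, and the missing tail counts as lower exposure under that dietary state.

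AUC0-tlast is also the declared measure least protected from this. A short profile tends to fail the terminal-phase rule, which removes AUC0-inf and leaves AUC0-tlast as the only declared AUC endpoint for that profile.

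The cohort is 12 people with advanced cancer, with samples due at about 24, 48 and 72 h after each of two doses. Protocol 4.1.2 allows the fasting restrictions to be reconsidered on the Part 1B results, so the ratio has a use.

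**Working it through.** **1. The plan's own precision figure.** Protocol Table 14 gives bounds for the 90% interval with n = 6 per sequence. With sw = sqrt(ln(1 + CV²)), 10 degrees of freedom, t = 1.8125 and sqrt(chi-square(0.80; 10)/10) = 1.1594, the log half-width is 1.8125 × SE × 1.1594. For CV 20%, sw = 0.198. Taking SE = sqrt(2) × 0.198 × sqrt(2/6) = 0.162 gives a half-width of 0.340. That is 35.6% to 70.2% at a ratio of 0.50, as printed, and all nine rows reproduce to rounding.

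The usual 2×2 crossover SE is sw × sqrt(1/6) = 0.081, half of this. Table 14 is therefore conservative if the CV is truly within-participant. That is a separate matter; the checks below use the crossover SE.

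**2. Which rules would catch a short profile?**

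| Rule | Trigger | Reaches a short AUC0-tlast? |
|---|---|---|
| SAP 16.1.4, pre-dose value | Pre-dose above 5% of Cmax | No |
| SAP 16.1.4, important deviations | Deviation likely to affect PK | Only if so classified; 10.2.1 does not name missed terminal samples or withdrawal |
| SAP 10.2.1, Data Review Meeting | Case by case, open list | Possibly, by discretion |
| SAP 16.1.5.1, terminal phase | Extrapolation, fit, span | No; AUC0-inf and related parameters only |

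With absorption ignored, a profile ending at 24 h has an extrapolated share of 6.2%, 25% and 50% for half-lives of 6, 12 and 24 h. At 12 and 24 h the 20% limit removes AUC0-inf while AUC0-tlast stays.

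**3. Size of the shift.** The half-life is an assumption. The washout text (five half-lives, at most 6 days) is compatible with up to 144/5 = 28.8 h; 6, 12 and 24 h are used here. With one-compartment kinetics, k = ln 2 / half-life and an assumed ka of 1/h, AUC(0–T) is proportional to (1 − e^(−kT))/k − (1 − e^(−ka·T))/ka. The share is AUC(0–T)/AUC(0–72). With 6 per sequence each participant carries weight 1/12 in the log ratio, so one truncated fed profile multiplies a true ratio of 1.00 by share^(1/12).

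| Fed sampling ends at | Share (6 / 12 / 24 h) | Ratio, one of 12 |
|---|---|---|
| 48 h (72 h sample lost) | 0.996 / 0.949 / 0.852 | 1.000 / 0.996 / 0.987 |
| 24 h | 0.930 / 0.747 / 0.557 | 0.994 / 0.976 / 0.952 |
| 10 h | 0.644 / 0.411 / 0.262 | 0.964 / 0.929 / 0.894 |

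Example: 0.411^(1/12) = exp(−0.889/12) = 0.929. Ignoring absorption changes these ratios by less than 0.01. Two fed profiles ending at 10 h give 0.93 / 0.86 / 0.80.

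**4. Interval (simulated crossover, CV 20%, 40,000 runs).** With no truncation the typical 90% interval is the estimate times or divided by 1.15. One fed profile ending at 24 h with a 24 h half-life makes that 1.18, and coverage stays near 90%. Two such profiles reduce coverage to about 85%. One fed profile ending at 10 h widens the log half-width by about 10%, 37% and 73% for the three half-lives.

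**5. Balanced losses.** If Period 2 is cut at 24 h for one participant in each sequence (24 h half-life), the mean ratio stays at 1.00 because the period effect absorbs the loss, and the interval factor rises from 1.15 to about 1.20.

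**The case against.** Much of the case on the other side stands.

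- **Planned windows are equal.** Period 1 runs to 72 h and Period 2 to the Day 4 pre-dose sample, also about 72 h. Only unplanned loss of terminal samples matters; a missed mid-profile sample does not shorten the window.
- **A fixed-interval AUC is already modelled.** AUCtau in SAP 16.1.3 is little affected by losses after 24 h, nor is Cmax, so a discrepancy with AUC0-tlast would show. AUCtau does not cover a profile that ends at 10 h.
- **A fixed-timepoint fallback exists** beside AUC0-tlast, but it is optional and tied to AUC0-inf being unreliable.
- **Truncation would be visible** in the reported tlast, the sampling-time listings and the overlaid fed and fasted profiles. Visibility does not say how the model should treat it.
- **Withdrawal in Period 1 leaves no within-participant comparison.** Such a value carries less weight: with a 12 h half-life and a 10 h cut, the ratio is about 0.978 to 0.990 (assumed between-participant SD 0.3 to 0.5), not 0.93.
- **The assessment is exploratory and preliminary**, with no stated acceptance limit, so no prespecified decision can be shown to change.

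A reader might infer that every profile in the PK analysis set enters the model. The exclusions in SAP 16.1.4 and the Data Review Meeting route contradict that; the accurate statement is that none of them is keyed to sampling length. A reader might also infer that any unequal sampling is reported as a food effect. It is not: the ratio is biased only when losses fall unequally on fed and fasted.

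**Conclusion.** The gap is real and narrow. As written, the SAP lets a period shortened by withdrawal or missed terminal samples enter the AUC0-tlast comparison against a full period, and nothing specific to sampling length prevents it. With 12 participants, balance of such losses between fed and fasted cannot be relied on.

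Losing only the 72 h sample in one fed profile moves the ratio by at most about 1.5%, even at a half-life of 28.8 h. The effect is material only for early truncation with a longer half-life: about 5% for one profile ending at 24 h and about 11% for one ending at 10 h, both at 24 h. These sizes rest on the assumed half-lives, one-compartment kinetics, CV 20%, a true ratio of 1.00 and losses in the fed state only.

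The problem lies in SAP 16.1.3, read with 16.1.4 and 16.1.5.1, more than in the protocol table, whose model sentence names Cmax and AUCtau. It calls for a cheap improvement to a stated method; it does not undermine the crossover analysis.

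**What to change.** In SAP 16.1.3, add for the AUC0-tlast food-effect comparison:

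- If a participant's sampling stopped early in one period through withdrawal or missed terminal samples, AUC is computed in both periods to the last nominal time sampled in both.
- A participant with only one period, and that one truncated, does not contribute AUC0-tlast to the model.
- AUC0-tlast as defined in 16.1.5.1 stays in the listings for these participants, flagged.
- Profiles sampled to 72 h whose late values are below the quantification limit are unaffected.

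Qualify the withdrawal sentence in 16.1.4 to match. With a common window the truncation factor cancels, and the expected ratio returns to 1.00 when there is no food effect.

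Replacing AUC0-tlast with AUC0-72 is not advised. It would change a declared endpoint, and for a truncated profile AUC0-72 would rest on an extrapolated concentration.

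The cost is SAP wording and one derivation, with no new data and no change in sample size. The downside is that the comparison for an affected participant covers a shorter window, or that one single-period value is lost.

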9.4.4 Sequence of Analyses

SMC for Part 1A: The SMC will review available data during study conduct. The cut-off for dose escalation assessments by the SMC will usually be triggered by the completion of the DLT period (or dropout) of the last participant in the respective dose escalation cohort of usually 3 participants. When enrolment of last participant in a dosing cohort is delayed, the SMC may decide (based on available data) upon enrolment and dose for the next dosing cohort before all participants in a cohort have completed 21 days. The Bayesian model will then be updated with the available data, and the data from the participant not having completed the DLT period at time of SMC will be considered in the next SMC. In these cases, cut-off can be earlier (after DLT period of the first 2 subjects is finished or they experienced a DLT).

SMC for Part 1B: The cut-off of the SMC will be triggered when the 6th participant has been treated for 28 days (or has dropped out). The SMC will be supported by the results of the Bayesian model used in Part 1A.

Primary analysis for dose escalation

The cut-off for an exploratory analysis of the safety, available PK, available Pd and preliminary antitumor activity data from Part 1A will be triggered when all participants have reached either the first on-treatment tumor assessment, or experienced death or premature withdrawal for any reason, whichever comes first.

Final Analysis for Part 1A and 1B

Follow-up analyses to report further efficacy, safety, and PK data if applicable for Part 1A and all analyses for Part 1B will be performed once the End of Study has been reached.

Additional Analyses

Further analyses may be performed, e.g. for publication purposes or decision-making purposes.

More details will be described in the iAP.

10

References

Curtin NJ. DNA repair dysregulation from cancer driver to therapeutic target. *Nat Rev Cancer*. 2012;12:801-17.

Appendix 1 Abbreviations

AE	adverse event
AESI	adverse event of special interest
ALT	alanine aminotransferase
aPTT	activated partial thromboplastin time
ATM	ataxia-telangiectasia mutated
ATR	ataxia-telangiectasia and rad3-related
BLRM	Bayesian 2-parameter Logistic Regression Model
CI	confidence interval
CRF	case report form
CSR	clinical study report
CV	coefficient of variation
CYP	cytochrome P450
DDR	DNA Damage Response
DL	dose level
DNA	deoxyribonucleic acid
DSB	double-strand break
ECG	electrocardiogram
FAS	full analysis set
γ -H2AX	gamma histone family member X
GCP	Good Clinical Practice
GMR	geometric mean ratio
HR	homologous recombination
iAP	integrated analysis plan
IB	Investigator's Brochure
ICF	informed consent form
ICH	International Council for Harmonization
IEC	Independent Ethics Committee
IRB	Institutional Review Board
IXRS	Interactive (phone and web) Response System
MTD	maximum tolerated dose

NCI-CTCAE	National Cancer Institute Common Terminology Criteria for Adverse Events
NHEJ	nonhomologous end-joining
p-ATM	phosphorylated ataxia-telangiectasia mutated
PD	disease progression
Pd	pharmacodynamics
P-gp	P-glycoprotein
PK	pharmacokinetics
PKAS	pharmacokinetic analysis set
PTEN	phosphatase and tensin homolog
QTcF	QT interval corrected using Fridericia's formula
RECIST	Response Evaluation Criteria in Solid Tumors
RDE	recommended dose for expansion
SAE	serious adverse event
SAF	safety analysis set
SCR	screening analysis set
SMC	Safety Monitoring Committee
STD	severely toxic dose
ULN	upper limit of normal
WOCBP	woman of childbearing potential

